## **Specific Aims**

- 1. Identify changes in brain function and structure that correlate with response to erenumab.** The objective of this aim is to investigate effects of treatment with erenumab on brain function and structure in patients who respond to treatment with erenumab and in patients who do not respond to treatment with erenumab. Specifically, this aim will assess changes in brain structure (cortical thickness, volume, area, white matter integrity), brain perfusion, resting-state functional connectivity, and pain-induced brain activation patterns in treatment responders and in treatment non-responders. This aim will identify structural and functional brain biomarkers for treatment response with erenumab.
- 2. Develop models to predict which patients will respond to erenumab.** The goal of this aim is to identify structural and functional brain magnetic resonance imaging predictors of response to erenumab in patients with migraine. Specifically, this aim seeks to identify those migraine patients who are going to have a positive response to erenumab treatment versus those who will not respond to treatment. Pre-treatment and early post-treatment imaging data will be used separately, and also in combination, for predictive modeling.

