### Sample Size

The total sample size of 50 patients accounts for the likely scenario in which up to 15% of patients will not have full datasets due to loss-to-follow-up or unusable MRI data (e.g. patient motion, abnormal brain MRIs). Based upon the results of the phase 2 and 3 trials of erenumab and the fact that this is an open-label study, we anticipate that approximately 50% of patients will be “responders” at 8 weeks. (6-8) Thus, we would have at least 21 responders and 21 non-responders for this analysis, a sample size that is adequate for the imaging and multivariate modeling aims of this study. Sample size was determined by calculating the number of subjects needed per group to detect a difference in pain induced BOLD signal of 0.1% pre-erenumab to post-erenumab, assuming a standard deviation of 0.1. Based on a type I error of .05, a sample size of 21 patients per group will give 88% power to detect pre-treatment to post-treatment differences for responders and non-responders. The use of % signal change as the measure for calculating effect size is the standard recommendation when determining sample size for fMRI studies.(41)

Desmond and Glover, in their paper entitled “Estimating sample size in functional MRI (fMRI) neuroimaging studies: statistical power analyses”, used data from fMRI studies of cognitive function and somatosensory stimulation to estimate sample sizes needed for fMRI studies. [Desmond 2002] They concluded that for a threshold of 0.05, about 12 subjects are required to achieve 80% power at the single voxel level for typical activations. However, they state that at more realistic thresholds that approach those used after correcting for multiple comparisons, the number of subjects doubles (n=24) to maintain this level of power.

As Mumford and colleagues point out, the number of stimulations/events that are included in the fMRI paradigm must also be considered when calculating power – the more stimulations/events, the greater the power to detect a difference.(41)

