*Specific Aim #2 (i.e. Develop models to predict which patients will respond to erenumab):* Pre-treatment scans will be used to identify MRI predictors of erenumab response. Multivariate machine-learning modeling of brain structural and functional data will be utilized for developing the predictive model. Because there are many imaging features available, but only a limited set of patients for this analysis, principal components analysis (PCA) will be performed on features collected from each imaging type to reduce the dimensionality of the data. The principal components (PCs) that result from PCA are linear combinations of the original imaging features, and can consolidate the information from the original features in such a way that only a few PCs are needed to explain most of the data variance. PCA will be performed separately on features from each imaging type to enhance clinical interpretability of PCs chosen for the predictive model.

To maximize the prediction accuracy, we will employ an ensemble learning approach by including a number of contemporary and complementary machine learning algorithms for building the predictive model, including Linear Discriminant Analysis (LDA), Quadratic Discriminant Analysis (QDA), Support Vector Machines (SVM), and Decision Tree (DT). Integrating these algorithms with Particle Swarm

Optimization (PSO)-based feature selection, we will identify the subset of features (PCs) that maximizes cross-validated accuracy of predicting responders and non-responders. Feature selection is a key step to avoid overfitting when building a predictive model with limited samples. PSO is a bio-inspired optimization algorithm that mimics the collective and collaborative behavior of social swarms in nature, e.g., colonies, honeybees, and bird flocks, in finding the optimal feature subset, and has been shown to outperform conventional feature selection algorithms in numerous recent publications.

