Additionally, noting that this study will collect both widely accessible imaging data such as that derived from T1-weighted sequences as well as less accessible types such as pain-induced functional activations, we aim to determine how widely useable our predictive model is in clinical practice. To achieve this goal, we will first limit our PSO-based feature selection to select only PCs derived from structural measures of T1-weighted sequences. Then we will compare the accuracy to that of another analysis allowed to select resting state functional connectivity data, followed by selection of additional PCs from more advanced imaging data. This result will help determine how much value is added when using advanced imaging data in predicting treatment response; and if advanced imaging is not available in a clinic, how good the predictive accuracy can be.

Patient characteristics, cognitive function, and sensory thresholds can also be included in predictive models.

*Safety Analysis:* The proportion of subjects experiencing adverse events, the nature of the adverse events, as well as severity and relationship of the adverse events to the study will be reported using descriptive statistics. The proportion of subjects with adverse events that led to withdrawal from the study will also be reported. All subjects who received at least one dose of erenumab will be included in the safety analysis.

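### Aim 2 defines only the cross-validated accuracy that its own search maximises: if reported, that figure is biased upward, and the imaging-tier comparison is confounded with search size

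*Combined protocol and SAP*

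**What the plan says.** Under Analysis Plans, Specific Aim #2, principal components analysis (PCA) is run separately on each imaging type, in the expectation that "only a few PCs are needed to explain most of the data variance". An ensemble of LDA, QDA, support vector machines and decision trees is then combined with PSO: "we will identify the subset of features (PCs) that maximizes cross-validated accuracy of predicting responders and non-responders". On overfitting the plan states: "Feature selection is a key step to avoid overfitting when building a predictive model with limited samples".

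The search is first restricted to PCs from T1-weighted structural measures. "Then we will compare the accuracy to that of another analysis allowed to select resting state functional connectivity data", and PCs from more advanced imaging follow. Of this comparison the plan says "This result will help determine how much value is added when using advanced imaging data in predicting treatment response", and also, "if advanced imaging is not available in a clinic, how good the predictive accuracy can be".

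Specific Aims adds further model sets: "Pre-treatment and early post-treatment imaging data will be used separately, and also in combination, for predictive modeling". Sample Size gives the patients available: "we would have at least 21 responders and 21 non-responders for this analysis".

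The plan does not give the number of PCs per imaging type, the number of folds, the swarm settings, the rule for combining the four algorithms, or an interval for accuracy.

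**The concern.** The cross-validated accuracy of one model fixed in advance is a fair estimate of its performance. The highest such value among many candidate subsets is not, because the same patients' outcomes both choose the winner and score it. The plan presents feature selection as protection against overfitting, but here selection is driven by the outcome labels and is itself the source of optimism.

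The tier comparison has a second problem. Each wider pool offers more subsets to try, so part of any rise in accuracy comes from searching more.

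Two practical answers are at stake: how much advanced imaging adds, and what a clinic with only T1 imaging could expect. Aim 2 is one of the study's two Specific Aims.

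**Working it through.** **The plan's own figures.** Aim 2 has no stated target accuracy, power or precision. The only power figure, 88% in Sample Size, concerns the Aim 1 BOLD difference. A two-sample t calculation (21 per group, difference 0.1, SD 0.1, two-sided 0.05) gives 88.5%, but this does not bear on Aim 2. The patient number is consistent: 50 × 0.85 = 42.5, about 21 per group at a 50% responder rate.

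**Logic of the tiers.** Let C(S) be the cross-validated accuracy of subset S on fixed folds, and A(P) the maximum of C(S) over all S within pool P. I read the tiers as cumulative, so P1 lies inside P2 and A(P1) ≤ A(P2). The best attainable value cannot fall when a pool is added. Only an incomplete swarm search or different folds can make it fall.

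**Size on pure noise.** Inputs from the plan are 42 patients split 21/21, so true accuracy is 50%. Everything else is assumed: independent normal PCs, LDA only, and the settings below.
- Simulation A: 5 imaging types, k PCs per type, tiers of k/2k/5k, 5-fold CV, exhaustive search up to 6 PCs and otherwise a swarm of 15 particles × 20 iterations, 300 data sets.
- Simulation B: 7-fold CV, 20 particles × 30 iterations, 80 data sets.

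| Candidate PCs by tier | Maximised accuracy, T1 / + resting-state / all (%) | Gain, T1 to all (points) | Nested CV (%) |
|---|---|---|---|
| A, 2/4/10 | 55.8 / 61.0 / 69.0 | +13.2 | not run |
| A, 3/6/15 | 59.3 / 65.0 / 71.9 | +12.5 (positive in 94%) | 49.8 / 50.4 / 49.6 |
| A, 5/10/25 | 63.7 / 69.3 / 73.7 | +10.0 (positive in 90%) | 50.6 / 50.8 / 50.7 |
| B, 5/10/15 | 62.9 / 68.9 / 72.3 | +9.4 (positive in 96%) | 48.2 / 48.7 / 49.1 |
| B, 10/20/30 | 70.1 / 75.1 / 76.0 | +5.9 (positive in 75%) | 50.5 / 51.2 / 50.1 |

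Bias in level runs from 55.8 − 50 = 5.8 to 76.0 − 50 = 26.0 points. More PCs raise the level but reduce the false gain.

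Exhaustive search with 3 and then 6 noise PCs, which removes swarm failure, gave about 59% and 65%. The larger pool was never lower, and was strictly higher in 67% to 72% of data sets.

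**Bias in the gain when signal exists.** Bias = (apparent all − apparent T1) − (true all − true T1), where true accuracy is that of the rule selected and refitted on the 42 patients. Signal sits on one PC; class means differ by the stated SD (Simulation A).

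| Signal | Bias, k = 3 (points) | Bias, k = 5 (points) |
|---|---|---|
| T1 1 SD only | +12.5 | +13.4 |
| T1 2 SD only | +9.3 | +11.2 |
| Advanced 1 SD only | +7.6 | +6.2 |
| Advanced 2 SD only | +1.5 | +1.1 |
| Advanced 3 SD only | −2.8 | −4.1 |
| T1 1 SD + advanced 1 SD | +10.8 | +11.1 |
| T1 1 SD + advanced 2 SD | +6.2 | +6.5 |

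For T1 1 SD only with k = 3, apparent accuracy rises from 71.4% to 78.9% (+7.5) while true accuracy falls from 66.8% to 61.8% (−5.0). Simulation B, 10/20/30 PCs, agrees: apparent 77.8% to 82.0% (+4.2), true 64.2% to 59.2% (−5.0). The T1-only figure itself is too high by 71.4 − 66.8 = 4.6 points in A and 77.8 − 64.2 = 13.6 in B.

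Nested CV in Simulation A had a bias in the gain of −2.8 to +0.2 points over the no-signal case and the seven signal scenarios, with k = 3 and 5.

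**Four algorithms, noise, one pool.** With 3 PCs: LDA 59.1%, best of four 63.4%, majority vote 58.9%. With 5 PCs: 61.9%, 66.8% and 62.9%. Extra inflation therefore depends mainly on whether the best algorithm is picked or the four are combined. The four were not run through the tiers.

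**The case against.** The strongest reply is that this is an omission rather than a stated error. The Analysis Plans give a criterion for choosing PCs, and the inner loop of a nested design would use the same one. A reader might infer that the plan commits to reporting the maximised value. It does not say so, and the harm depends on that value being used. What remains is that the plan defines no other accuracy and goes on to compare accuracies across tiers.

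The plan's wording is also measured. It calls feature selection a key step, not the only one, with PCA also reducing dimensionality, and it says the comparison will help determine added value.

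The sizes depend on assumptions. PC counts, folds and swarm settings are mine, and the tier results use LDA only. The false gain roughly halves between the smallest and largest pools tried, so the range matters more than any single figure. Modelling early post-treatment and combined data, and optional clinical variables, could widen the search further; I did not simulate this.

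Two further readings go too far. One is that the tier comparison always favours advanced imaging: with strong advanced signal the bias is near zero or negative. The other is that the fall in true accuracy shows added imaging to be harmful. In that scenario the added PCs carry no information either way; the fall is the cost of selecting noise PCs with 42 patients.

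Finally, nested CV will not make the tier question easy to answer with this sample. That is correct and belongs in the reporting.

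**Conclusion.** The point holds conditionally. If the maximised accuracy is reported, it is biased upward: about 56% to 76% on average with no signal, against a true 50%. The tier comparison mixes added signal with search size, giving a false gain of about 6 to 13 points on pure noise. The bias becomes smaller with moderate advanced signal and can turn negative with strong signal. When only T1 carries signal, the apparent gain can have the opposite sign to the change in true accuracy of the rule selected on 42 patients.

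The direction on noise follows from the logic of the search. The sizes rest on the assumed PC counts, folds and swarm settings, on independent normal PCs and on LDA. The plan attaches no accuracy threshold to Aim 2, and the Aim 1 primary analysis is not affected. The gap should be closed before Aim 2 is analysed.

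**What to change.** Specify nested cross-validation for Aim 2:

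- Within each outer training fold, repeat PCA, PSO selection and the choice or combination of the four algorithms. Report accuracy only from the outer test folds.
- Compare the T1-only, resting-state and advanced tiers on the same outer folds.
- State in advance the number of PCs per imaging type, the folds, the swarm settings and the rule for combining algorithms.
- Obtain intervals from repeated nested CV, resampling or permutation of the whole pipeline. A binomial standard error, √(0.25/42) = 7.7 points near 50%, is too small: nested accuracy had an SD of about 9 to 11 points across simulated data sets.
- Report the tier comparison as an exploratory estimate with its interval.

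The cost is computing time and plan wording; no new patients or scans are needed. Reported accuracies will be lower and less precise. They will also be slightly low where signal exists, since with five outer folds each outer model is trained on about 80% of patients. On noise the nested T1-to-all gain had an SD of 12.4 points (k = 3) and 11.4 points (k = 5). Twice these values is 24.8 and 22.8 points, so true gains below roughly 23 to 25 points may not be resolved.

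### Aim 2 selects and judges its prediction models on raw accuracy alone, which credits predicting the larger class whenever responders and non-responders are unequal in number

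*Combined protocol and SAP*

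**What the plan says.** All three steps of Aim 2 in the Analysis Plans section use the same measure.

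- Model building: "To maximize the prediction accuracy, we will employ an ensemble learning approach", combining LDA, QDA, SVM and a decision tree.
- Feature selection: "we will identify the subset of features (PCs) that maximizes cross-validated accuracy of predicting responders and non-responders".
- Comparison of imaging tiers: after a model limited to T1 structural measures, "Then we will compare the accuracy to that of another analysis allowed to select resting state functional connectivity data", and then more advanced imaging is added. Usability is judged by "if advanced imaging is not available in a clinic, how good the predictive accuracy can be".

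The section does not mention sensitivity, specificity, balanced accuracy, the area under the ROC curve, class priors or weights, or a no-information benchmark.

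The class split is only expected. The Sample Size section says "we anticipate that approximately 50% of patients will be" responders at 8 weeks and concludes that "we would have at least 21 responders and 21 non-responders for this analysis". The Daily Headache Diary section also leaves room for a different definition of response once outcomes are known, which could move the split again.

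**The concern.** Response is observed after treatment, so enrolment cannot balance it. If the classes are unequal, a rule that puts every patient in the larger class scores that class's share as accuracy, yet cannot separate anyone. Raw accuracy therefore mixes real discrimination with credit for the class split. A classifier that takes its class priors from the data will also label too many patients with the larger class, and an accuracy figure on its own does not show this.

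The aim is to tell responders from non-responders. A model could post a respectable accuracy while misclassifying most of the smaller group. This is a different problem from optimism due to selecting and reporting on the same cross-validation: it remains when the model is applied to new patients.

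**Working it through.** **Inputs.** From the Sample Size section: 50 patients ("The total sample size of 50 patients accounts for the likely scenario"), loss of "up to 15% of patients will not have full datasets due to loss-to-follow-up or unusable MRI data", and about 50% responders. Assumed, because the documents do not give them: true response rates of 40% and 60%, and all simulation settings.

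**1. The plan's class sizes.** 50 × (1 − 0.15) × 0.5 = 21.25 per class, so 21 and 21 is reproduced, with 42 evaluable patients.

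**2. How often the split is unequal.** With K responders distributed Binomial(42, p), the larger-class share is max(K, 42 − K)/42.

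| True rate p | Mean larger-class share | P(exactly 21:21) | P(25:17 or worse) | P(28:14 or worse) |
|---|---|---|---|---|
| 50% | 56% | 12% | 28% | 4% |
| 40% or 60% (assumed) | 61% | 5% | 60% | 24% |

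**3. A rule with no information.** Always predicting the larger class has raw accuracy 21/42 = 50% at 21:21, 25/42 = 59.5% at 25:17 and 28/42 = 66.7% at 28:14. Its balanced accuracy is (100% + 0%)/2 = 50% at every split.

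**4. A fitted model with no information.** Simulation on pure noise: 8 PCs, LDA, 7-fold cross-validation, best subset of up to 3 PCs. New patients have the same split. Sensitivity refers to the larger class; figures are approximate.

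| Split | LDA priors | Subset chosen on | Cross-validated sensitivity / specificity | Accuracy in new patients |
|---|---|---|---|---|
| 21:21 | empirical | accuracy | 67% / 68% | 50% |
| 25:17 | empirical | accuracy | 86% / 41% | 54% |
| 28:14 | empirical | accuracy | 95% / 25% | 63% |
| 28:14 | equal | accuracy | 68% / 65% | 51% |

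The new-patient figures agree with their components. At 28:14, one run gave 87% sensitivity and 13% specificity in new patients: (28 × 0.87 + 14 × 0.13)/42 = 26.18/42 = 62%. At 25:17 it gave 73% and 27%: (25 × 0.73 + 17 × 0.27)/42 = 22.84/42 = 54%. Balanced accuracy is 50% in both cases, as it should be for noise.

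**5. Where the skew comes from.** At 28:14 with empirical priors, the average over all subsets before any search is already about 91% / 9%. Choosing the subset on accuracy raises specificity to about 25%. Choosing it on balanced accuracy gives about 92% / 31%. Keeping raw accuracy but setting equal priors gives 68% / 65%. The priors, more than the selection target, produce the skew.

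**6. Other settings.** With 20 noise features, 5-fold cross-validation and 200 random subsets, unselected accuracy was 50%, 56% and 67% at 21:21, 25:17 and 29:13, with balanced accuracy about 50% throughout.

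**The case against.** The strongest reply has five parts.

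- *The plan expects equal classes.* At 21:21 raw and balanced accuracy coincide, and 28:14 or worse has probability only 4% at a true rate of 50%. This stands as a limit on size. But an exact 21:21 split has probability 12%, and the plan contains nothing to protect it if the rate differs from 50%.
- *The search is not the cause.* A reader might infer that maximising accuracy drives feature selection towards the larger class. Step 5 does not support that: the search moved the null model slightly away from it. The skew depends on the priors, on which the plan is silent, so equal priors come first in the remedy.
- *Most of the inflated cross-validated accuracy is something else.* The selected null models show 67% at 21:21 and 72% at 28:14. Since 67% arises with no imbalance, most of the excess is selection optimism, a separate matter. Only the new-patient accuracy and the gap between sensitivity and specificity count here.
- *The tier comparison largely survives.* A reader might infer that it is invalid. All tiers predict the same outcome in nominally the same patients and share one majority baseline, so a difference is distorted only if tiers lean towards the larger class to different degrees.
- *Chance level can be worked out.* Any reader with the responder counts can compute the majority share. True, but that does not reveal how the errors fall between the classes.

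A reader might also set the result against the 75-86% accuracies under Published Work and Preliminary Data. The plan proposes no such benchmark, and those figures concern diagnosis, so they add nothing to this point.

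**Conclusion.** The point holds, conditional on unequal classes. Raw accuracy is the only stated measure for Aim 2, and it credits a no-information model by an amount that depends on a split nobody controls. For a constant rule the credit averages about 6 percentage points above 50% from chance imbalance at a true rate of 50%, and about 11 points at 40% or 60%. For a noise-fitted LDA with empirical priors it is about 4 points at 25:17 and 13 points at 28:14 in new patients, and it almost disappears with equal priors. At 21:21 it is nil.

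The binomial figures rest on 42 evaluable patients and the stated response rates. The simulation rests on assumed numbers of PCs and folds, an assumed search, and LDA alone; the plan's particle swarm search and full ensemble were not reproduced. The primary analysis, which belongs to Aim 1, is untouched. This is a low-cost improvement that should be made before modelling starts.

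**What to change.** In the Aim #2 text of the Analysis Plans section:

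1. Set equal class priors or class weights in LDA, QDA, SVM and the decision tree. This removes most of the skew.
2. Make balanced accuracy, or the area under the ROC curve, the quantity that feature selection maximises and on which the imaging tiers are compared.
3. Report sensitivity, specificity and the majority-class rate beside any raw accuracy, including the T1-only model used to judge usability in ordinary clinics.

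This needs no new data, patients or visits: it changes an objective function and a weighting option, and adds a few reported columns. The downside is that the headline figure may be lower when the classes are unequal. If they turn out equal, nothing is lost.

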## **Background**

Migraine is a highly prevalent disorder that affects 38 million people in the US and is associated with moderate to severe pain, hypersensitivities to sensory stimuli, nausea, vomiting, and reduced quality of life. (1-3) Annual costs from migraine are estimated at \$20 billion in the United States and €27 billion in Europe. (4, 5) Migraine remains poorly treated and there are currently few options for the preventive treatment of migraine. The release of erenumab to the market represents a substantial improvement in the landscape of migraine preventive treatment.

Phase 2 and 3 randomized, double-blind, placebo-controlled studies have demonstrated that erenumab is safe and effective for the prevention of episodic and chronic migraine. (6-8) Erenumab received US Food and Drug Administration approval for the prevention of migraine in May 2018. Structural and functional neuroimaging could provide important insights into central mechanisms of treatment response and imaging biomarkers that track treatment response or are indicators for early treatment response. A few studies have demonstrated normalization of functional activation patterns, reorganization of functional connectivity, and normalization of brain metabolism following migraine treatment with external trigeminal neurostimulation, topiramate, and precision ophthalmic tints. (9-12) However, the effects of erenumab on brain function and structure, including the processing of painful stimuli, have been inadequately investigated. Furthermore, it is possible that measures of brain function and structure could serve as predictors for clinical response to erenumab, either prior to treatment or early after the first treatment. It is of clinical interest to interrogate whether neuroimaging is a useful technique for establishing a brain biomarker for predicting treatment response and measuring treatment responses earlier than is possible using clinical measures alone.

This study will investigate longitudinal changes in brain structure and function in high frequency episodic migraine and chronic migraine patients who are responding to erenumab treatment compared to those patients who are non-responders. In addition, pre-treatment and early post-treatment brain imaging data will be used to build models that predict which individual migraine patients will respond to erenumab treatment.

[figure not shown]
The Specific Aims of this study are to:

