#### Daily Headache Diary

A daily headache diary will be completed for the next 12 weeks to allow for assessment of changes in headache and migraine frequency. Headache diary data will be analyzed to classify patients as “responders” (50% or greater reduction in migraine day frequency between weeks 5-8 post first erenumab treatment compared to frequency during the run-in phase) or “non-responders” (less than 50% reduction in migraine day frequency during weeks 5-8 post first erenumab treatment compared to the frequency during the run-in phase). Since patient outcome will be measured at 8 weeks (opposed to 12 weeks like is done in the majority of clinical trials), depending upon patient outcomes other definitions of “response” and “non-response” could be used. Furthermore, correlations between changes in migraine frequency and imaging outcomes could also be assessed.

A migraine day will be defined as follows: any calendar day during which a person experiences a qualified migraine headache (onset, continuation, or recurrence of the migraine headache). A qualified migraine headache is defined as a migraine with or without aura, lasting for at least 30 minutes, and meeting at least one of the following criteria (a and/or b):

- a) At least 2 of the following pain features: unilateral, throbbing, moderate to severe, exacerbated with exercise/physical activity
- b) At least 1 of the following associated symptoms: nausea and/or vomiting, photophobia and phonophobia

If the participant takes a migraine-specific medication (i.e. triptan or ergotamine) during aura or to treat headache on a calendar day, then it will be counted as a migraine day regardless of the duration and pain features/associated symptoms.

Missing values may exist in headache dairy data due to various reasons such as subjects’ missed recording, early withdrawal, or inadequate entries prohibiting evaluation of the end point (responder vs. non-responder). To impute the missing data and allow for evaluation of migraine frequency,

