## **Two Week Follow-up Headache Characteristics**

How many days since baseline visit with headache of any kind/severity:

How many days since baseline visit with complete headache freedom:

Intensity:

Average on 0 (no pain) to 10 (most severe pain) scale: /10

Maximum on 0 (no pain) to 10 (most severe pain) scale: /10

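### Aim 2 has no clinical-only reference model, so as written it would not show whether imaging, chiefly the week-2 scan, adds to clinical data already collected

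*Combined protocol and SAP*

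**What the plan says.** The Background gives the purpose: to find out whether imaging can serve as a biomarker for predicting response and for "measuring treatment responses earlier than is possible using clinical measures alone". The Specific Aims section defines the predictor sets for Aim 2: "Pre-treatment and early post-treatment imaging data will be used separately, and also in combination, for predictive modeling".

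Analysis Plans, Specific Aim #2, sets out one accuracy comparison. It begins "we will first limit our PSO-based feature selection to select only PCs derived from structural measures of T1-weighted sequences". It continues: "Then we will compare the accuracy to that of another analysis allowed to select resting state functional connectivity data". Components from the more advanced sequences follow. The stated purpose is to learn "how much value is added when using advanced imaging data in predicting treatment response", and how good prediction can be in a clinic without such imaging.

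Non-imaging predictors get one sentence: "Patient characteristics, cognitive function, and sensory thresholds can also be included in predictive models".

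Early headache data are collected. On the diary: "A daily headache diary will be completed for the next 12 weeks to allow for assessment of changes in headache and migraine frequency". The two-week visit form asks "How many days since baseline visit with headache of any kind/severity", and the Case Report Forms schedule has the Patient Global Impression of Change at the same visit. None of these is named as a predictor or comparator in Aim 2. Response itself is defined from the same diary, as a reduction of at least 50% in migraine days in weeks 5-8 against run-in.

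**The concern.** A claim that imaging predicts response, or shows it early, is useful to a clinic only relative to what is known without the scan. At the week-2 visit that includes the run-in diary and about two weeks of post-treatment diary, which is the same instrument that later decides who is a responder. The early diary is therefore the natural competitor of the week-2 imaging model.

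The planned sequence starts at T1 structure, so its lowest reference is an imaging model and the only implicit reference below that is chance. Adding clinical variables to an imaging model does not help unless a model without imaging is reported alongside it. At stake is what Aim 2 can conclude: a good-looking accuracy could be reported although free diary data would have given much of it. The primary analysis of Aim 1 is not affected.

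**Working it through.** **1. The plan's own figure.** The Sample Size section gives 88% power for a BOLD difference of 0.1% with SD 0.1, 21 per group and type I error 0.05. Standardised effect d = 0.1/0.1 = 1. For a two-sample, two-sided t-test, df = 2 × 21 − 2 = 40 and the noncentrality is d√(n/2) = √10.5 = 3.24, giving 88.5%. The figure reproduces, but it belongs to Aim 1. For Aim 2 the section asserts that the sample is adequate and gives no calculation.

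**2. Patients available.** 50 × 0.85 = 42.5. With about 50% responders, that is 21 + 21 = 42.

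**3. What beating chance takes.** With a 21/21 split the chance rate is 50%. P(X ≥ 27 | n = 42, p = 0.5) = 0.044, one-sided, so 27/42 = 64% is enough.

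**4. What the diary alone might reach.** The documents give no figure, so this step is a simulation on stated assumptions:
- run-in rate uniform over 6-25 days per 28, with the eligibility range applied to the observed run-in count;
- true reduction with mean 45% and SD 35%, truncated (−20% to 100%), and binomial migraine days;
- early (weeks 1-2) and late (weeks 5-8) reductions correlated, with a given share of the effect present early;
- a logistic model on run-in days, weeks 1-2 days and their ratio, scored in a held-out half. About 49% are responders.

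| Share of effect present early | Early-late correlation | Accuracy | AUC |
|---|---|---|---|
| 100% | 1 | 79% | 0.88 |
| 100% | 0.7 | 69% | 0.76 |
| 100% | 0.5 | 64% | 0.69 |
| 100% | 0.3 | 59% | 0.62 |
| 60% | 0.3 | 58% | 0.61 |

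A differently built simulation (log-scale effects with SD 0.4-0.7, correlation 0.3-0.9, single best cut-off on diary change) gives 58-76% and AUC 0.61-0.83. A still slower onset goes lower: a quarter of the effect present early with correlation 0.4 gives 57% and AUC 0.59. Run-in days alone give 51%, by construction, because the simulated reduction does not depend on baseline frequency.

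**5. Steps 3 and 4 together.** With the full effect present early and a correlation of 0.5 or more, the diary alone reaches the 64% that beats chance.

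**6. Precision of the missing comparison.** One accuracy of 34/42 (81%) has an exact 95% CI of 66-91%. For two models scored on the same 42 patients, with 5-10% of patients correct only under the weaker one, exact McNemar power is 14-19% for 65% against 75% and 29-39% for 65% against 80%. Reaching 80% power would take about 155-234 and 85-120 patients respectively.

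**The case against.** The literal wording of Aim 2 is to develop imaging predictors, and the staged comparison answers a question the plan does pose: advanced against accessible imaging. The reference to clinical measures stands in the Background and, read naturally, qualifies measuring response earlier. This stands. A reader might infer that the plan promises imaging will predict better than clinical data; the documents do not say so. For the pre-treatment model, the only one that Analysis Plans describes in detail, a clinical comparator is good practice and its absence contradicts nothing. The case is strongest for the week-2 model.

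A reader might also infer that the trial is incapable of answering the question, or that clinical variables may enter only mixed with imaging. Neither follows. The diary, the two-week form and the global impression are all collected, and the permissive sentence neither commits to nor rules out a model without imaging. The gap is one of pre-specification.

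Finally, it is tempting to set the 79% beside the team's 75-86% imaging accuracies and say that the diary would do as well. That does not stand. The 79% needs early and late effects that are perfectly correlated and equal, with the second dose at week 4 changing nothing, and it was fitted in a very large simulated cohort. The 75-86% are for classifying diagnosis, not treatment response.

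**Conclusion.** The point holds in limited form. The Background sets imaging against clinical measures, the analysis compares imaging only with imaging, and nothing commits the team to a clinical-only reference. As written, Aim 2 would not show whether imaging, chiefly the week-2 scan, adds to data already in hand.

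The size is uncertain: about 58-79% accuracy (AUC about 0.61-0.88) from run-in plus weeks 1-2 diary data, for early-late correlations of 0.3-1 and 60-100% of the effect present early. A model fitted in about 42 patients would do somewhat worse. The simulation is silent on the baseline comparison, so it gives no ground for inferring that baseline clinical variables would rival pre-treatment imaging. The finding itself rests on the text and does not depend on any one simulated figure.

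**What to change.** Before analysis, make a clinical-only model the first step of the model sequence in Analysis Plans, Specific Aim #2.

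- **Baseline model:** run-in migraine days, episodic or chronic status, age, sex and years with migraine.
- **Week-2 model:** the same, plus the migraine-day rate over diary days up to the scan. A rate is needed because the visit window is 14 ± 2 days, so two full weeks are not always available.
- **Scoring:** evaluate clinical-only and clinical-plus-imaging models in the same outer cross-validation folds, with PCA and particle-swarm selection nested inside the training folds. The plan selects components to maximise cross-validated accuracy; comparing that optimised figure with a fixed clinical model would favour imaging.
- **Reporting:** give the gain in accuracy and AUC with a confidence interval, as an estimate and not as a powered test.

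The cost is one more model per time point, from data already collected, with no new visits or procedures. There are two downsides. The apparent value of imaging may shrink. And with about 42 patients the gain will be imprecise, so a small or null gain would not rule out added value; the report should say so.
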